The potential risks to participants are detailed as follows: Some participants may be uncomfortable answering questions about their past and/or current mental health, psychiatric symptoms, or risk behaviors (e.g., sexual behavior, substance use). Participants may also feel uncomfortable answering questions about their sexual attractions or their sexual and gender identity. However, it is important to note that an emotional discomfort is an event encountered routinely in daily life, and potential discomfort would likely not exceed what is typically encountered in these youths' experiences. All information

used in enrollment and recruitment describing the research activities will include a detailed description of the content and expected participation of the respondent, such that the respondent is aware of the nature of the questions to be included in the surveys.

2. Benefits:

SGM EA of color in the study may benefit through the process of developing their critical narratives with the potential to reflect on their experiences and behaviors. Furthermore, participation in the proposed study could potentially benefit participants in a few important ways. It is possible that the interview about their experiences and/or the CNI activity may be cathartic in nature as it may be the first time or opportunity allowing SGM EA of color to speak about their experiences. Others will benefit because the study will result in increased knowledge about narrative interventions to address mental health disparities among SGM EA of color and can inform interventions to address mental health concerns at large. In sum, the potential benefits of the research far outweigh the risks for the participants.

3. Subject Privacy:

Informed consent documents will inform research participants of the need to keep answers to questions confidential. Participants will have the option to refuse to answer or skip any questions on the surveys that they are uncomfortable answering. They will also be informed about the limits of confidentiality as it relates to imminent suicide risk or risk of imminent harm to others and the need to enact emergency procedures to ensure their safety and the safety of others. Psychological distress is a potential risk to SGM EA during the completion of the interviews or surveys, during the creation of their narratives, and during post-intervention visits (about one month after baseline).

We will need to collect a valid e-mail address to reimburse participants for their time (i.e., study incentives) and for internal auditing purposes. To ensure we have sent participants their incentives, we will keep the e-mail addresses in a list to be stored in a password-protected server. In addition, we will use participants' email, IP address, browser/operating systems, and time is taken to complete the survey to flag potential fraudulent/suspicious cases. We will crosscheck email and IP addresses through web applications (e.g., Facebook, IP lookup), yet we will not keep any of this information or link it to any behavioral data. We have taken this approach in prior studies and written on its importance for web survey research. Once identified, we will email suspicious cases and ask for clarification. If verified, we will treat each case as unique; otherwise, we will disqualify the case and not use the entered data.

Data will be stored in a secure environment, and all data files will have strong password protection. Access to data will be on a role-based standard; only those study staff that require access to identifying data to complete their study-related roles will be allowed access. All study staff will be trained in security and confidentiality procedures and will sign a confidentiality agreement before receiving access to any participant data. Contact information used to confirm participation will be held in a password-protected database on a University of Pennsylvania secure server, accessible only by study staff.

4. Subject Confidentiality

All participant data will be de-identified before analysis, and access to this information will only be available to research staff or on password-protected computer files. Audio recordings of participant interviews will be transcribed and de-identified and then destroyed to eliminate audible identification of subjects. Participants' contact information will be kept in a locked office accessible only to the research staff and on password-protected computer files housed within University servers.

How will confidentiality of data be maintained? Check all that apply.

- Paper-based records will be kept in a secure location and only be accessible to personnel involved in the study.
- Computer-based files will only be made available to personnel involved in the study through the use of access privileges and passwords.
- Prior to access to any study-related information, personnel will be required to sign statements agreeing to protect the security and confidentiality of identifiable information.
- Whenever feasible, identifiers will be removed from study-related information.
- A Certificate of Confidentiality will be obtained, because the research could place the subject at risk of criminal or civil liability or cause damage to the subject's financial standing, employability, or liability.

A waiver of documentation of consent is being requested, because the only link between the subject and the study would be the consent document and the primary risk is a breach of confidentiality. (This is not an option for FDA-regulated research.)

Precautions are in place to ensure the data is secure by using passwords and encryption, because the research involves web-based surveys.

Audio and/or video recordings will be transcribed and then destroyed to eliminate audible identification of subjects.

Other (specify):

Data will be kept for five years after the completion of the study (de-identified). Photos/videos of the narratives from participants will be kept for five years after the completion of the study. If participants choose to participate in the optional gallery after study completion, photos/videos will then be kept indefinitely. Please note that the gallery is an artistic endeavor and not an extension of the research (e.g., no data will be collected during/about the gallery).

Data from participants who fill out the eligibility survey – but are not eligible/do not enroll in the study will be kept within REDCap (HIPAA compliant survey application) until the completion of the study. Once the study has been completed, this data will then be deleted.

We will implement several strategies to offset the risks of loss of confidentiality related to data collection. To minimize the risk of participants feeling uncomfortable about answering personal questions, we will use self-completed online surveys for many of our assessments. Participants will input the answer to the question themselves and will be able to refuse to answer any question that makes them uncomfortable on either the self-report assessments or the in-depth interview. In interviews, participants will not be named and any additional reference to people and/or locations will be masked to increase their privacy. Once audio recordings of interviews have been transcribed and de-identified, they will be destroyed to prevent any audible identification of participants.

5. Protected Health Information

Participant-protected health information (PHI) will be collected, including Name, Telephone Number, IP address, and Electronic Mail address, for contacting participants throughout the study, including follow-up reminders. PHI of participants' date of birth will be utilized to determine age for eligibility (inclusion). Participants will also be audio recorded during their interviews. All interviews, after being transcribed and de-identified, will be destroyed.

6. Compensation:

Our incentive schedule will encourage assessment and interview completion, increasing the rates to encourage the completion of future study visits.

- At baseline for the completion of the survey and interview, participants will receive \$30.
 - To confirm eligibility at baseline, longitudinal and latitude data will be collected and required to receive compensation at baseline.
- At one month for the completion of the narrative, survey, and interview, participants will receive \$45.

Participants will be paid virtually using Greenphire Virtual Clincards; therefore, we will collect emails from each participant.

7. Data and Safety Monitoring:

The Principal Investigators will provide oversight of all study procedures and quality assurance checks. We have several mechanisms to ensure the security and integrity of the data. The intervention content, questionnaires, and personal information will be secured with role-based security that will provide different types of users with different access privileges. All printed records pertaining to the study containing collected data will be securely stored by the Principal Investigators in a locked metal file cabinet housed in the Department of Family and Community Health. No names or other identifying information appear on data documents or in data files, as the re-contact information will be stored separately. Electronic files and records will be stored in a firewalled, encrypted server at the University of Pennsylvania; only research staff will have access to this directory.

All staff will complete human subjects research training and data safety training as part of their project onboarding. To ensure participants' safety as well as the data's validity and integrity, only staff with extensive experience with SGM youth and

suicide prevention will be hired. All staff will have signed a confidentiality agreement. The Principal Investigators and Project Director will monitor staff closely. Staff deficient in any aspect of performance will be re-trained, closely monitored for proficiency, and if not adhering to established protocols and procedures, will be terminated. Only designated staff will have access to the data. The Principal Investigators and Co-Investigators will be responsible for disseminating study findings through presentations and publications. The Principal Investigators will also be solely responsible for handling any requests from other investigators to examine the data collected during this study.

If a participant (enrolled) or prospective participant reports suicidality or another intent to harm, we will have to break confidentiality. We will inform the participant of this verbally and within the consent form. We will note that we may need to break confidentiality for their safety if they report suicidality or other intent to harm. This may include contacting emergency contacts that they provide to us, putting them in contact with a study clinician, or calling 9-1-1 to have emergency response service be put in contact with them.

8. Investigator's Risk/Benefit Assessment:

No more than minimal risk: The risks to research participants enumerated above are reasonable in relation to the anticipated critical narrative creation among sexual minorities emerging adults of color. Our study is expected to result in benefit to society since it will provide a basis of knowledge on interventions for fostering participants' social support and empowerment to help them lower their mental health risks. Thus, the unlikely risks entailed by participation in this study are offset by its potential benefits.

INFORMED CONSENT:

1. Consent Process:

Potential participants will be directed to a website that will include a brief description of the study and a link to a short online eligibility screener. Participants will be asked to consent to an eligibility screener. The eligibility screener consent form will first ask the participant to answer yes or no to whether they consent to the screener. The eligibility screener consent will outline the voluntary nature of the survey, the participant's freedom to discontinue the survey at any time, approval to retain email addresses to send incentives, outline the use of the data being collected within the eligibility screener, and procedures to guarantee confidentiality. We will also collect latitude and longitudinal data to confirm the eligibility criteria of the participant living in the United States for eligibility. The data from the eligibility screener will allow us to retain all data from these screeners and compare/contrast who sought to enroll in the pilot study. Potential participants that are eligible based on inclusion criteria will be contacted by a study team member and scheduled for a baseline visit.

During the baseline visit, potential participants will be asked to complete a study consent form and sign it online through REDCap. A study team member will first go through the consent form with the participant and be available to answer any questions. The consent outlines the voluntary nature of the study, the participant's freedom to discontinue the study at any time, and approval to retain data for future research. Participants will also be informed that longitudinal and latitude data will be collected and required for confirmation of eligibility and compensation for the study. Participants will then indicate whether they consent or do not consent to participate in the study by filling out the REDCap form and checking a box of either "Yes, I do consent" or "No, I do NOT consent." Participants that do consent will sign the form electronically and be given the option to receive a signed pdf of their consent form via email.

2. Waiver of Informed Consent:

N/A

RESOURCES NECESSARY FOR HUMAN RESEARCH PROTECTION:

We have both the physical and virtual infrastructure necessary to carry out this project and ensure the protection of human subjects. We have locked filing cabinets to keep paper records, but the default will be using REDCap for data entry. As noted in the protocol, our team is comprised of professionals with expertise in conducting research with youth, sexual and gender minorities, and racial/ethnic minorities through technology-assisted interventions.

References:

Botfield, J. R., Newman, C. E., Lenette, C., Albury, K., & Zwi, A. B. (2018). Using digital storytelling to promote the sexual health and well-being of migrant and refugee young people: A scoping review. *Health Education Journal*, 77(7), 735–748. <https://doi.org/10.1177/0017896917745568>

Harris A (2013). Animating failure: Digital collaboration at the intersection of sex, race, and culture. *Continuum* 27: 812–824

Hennink, M., & Kaiser, B. N. (2022). Sample sizes for saturation in qualitative research: A systematic review of empirical tests. *Social Science & Medicine*, 292, 114523. <https://doi.org/10.1016/j.socscimed.2021.114523>

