PRINCIPAL INVESTIGATOR: [name]. & [name].

PROTOCOL TITLE: Sexual and Gender Minority Emerging Adults Eliciting Narratives (SEEN)

INTRODUCTION AND PURPOSE:

In the U.S., emerging adults (EA; ages 18-24) are a particularly vulnerable population for mental health concerns, including an increased rate of death by suicide and high rates of mental health symptoms (e.g., depression and anxiety). Youth who identify as sexual and/or gender minorities (SGM) are three times as likely to have made a suicide attempt compared to their heterosexual peers. The transition into adulthood for SGM EA in the United States, along with stressors of stigma experiences as a sexual minority and/or gender minority, may contribute to the disproportionate mental illness risk, specifically depression, suicidal ideation, anxiety, and substance use compared to their peers (Swann et al., 2020; Tan et al., 2017). These disparities are especially pronounced in SGM EA of color (racial/ethnic minorities). SGM communities of color are disproportionately affected by mental health outcomes of depression, anxiety, and suicide risk compared to their peers due to multilevel experiences of stigma at the intersections of ethnicity, race, gender, and sexual orientation. As a critical health disparity population designated by NIH, it is crucial to develop and test interventions that address SGM communities' social and behavioral health, particularly those with multiple marginalized identities.

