Critical Narrative Interventions (CNI) are group-based interventions that provide a space for narratives developed by marginalized communities to prompt dialogue intra- and inter-personally and stoke new thoughts, ideas, and actions to promote change. CNIs include various narrative forms, such as photography, digital stories, graphic novels, comics, and film. In a scoping review (Botfield et al., 2018), digital storytelling as a CNI for culturally diverse young people explored issues of racism and sexual and gender identity discrimination (Harris, 2013), sexual reproductive health promotion for U.S. Native American young people (Markus, 2012), and health promotion for positive youth development in Alaskan Native young people (Wexler et al., 2013). Each of these studies reported that developing digital stories was an empowering process, including increased knowledge, self-efficacy, and confidence. The increase in self-empowerment through participation in the critical narrative intervention was also replicated in photovoice studies (Budig et al., 2018). In a recent study, researchers followed up with photovoice participants in Spain to explore their experiences (Budig et al., 2018). Female participants experienced changes in empowerment through increased knowledge and skills, a change in self-perception, and access to resources. Participants noted that after developing their story they felt empowered to speak their truth and seek out social support (Budig et al., 2018).

Critical Narratives (CNs) have typically involved a group format as an intervention; however, CNs have the potential to be scalable and incorporated as an elicitation strategy for increasing empowerment (gaining knowledge and skills and increasing self-esteem) and seeking out social support as an individual strategy.

This pilot study will explore individual critical narratives (CNs) for SGM EA of color feasibility as a scalable strategy to 1) increase self-empowerment, 2) elicit intentions to seek social support, and 3) address psychological outcomes (i.e., depression, anxiety, self-esteem, empowerment, and psychological well-being).

Participants for this pilot are emerging adults living with depression who self-identify as both an SGM and a racial/ethnic minority. Participants will develop a critical narrative based on their randomized condition: photo-novella or digital story (determined to be methods that are easily scalable digitally).

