There is a need to develop interventions for SGM EA of color that empower them to seek out support and treatment for their mental health concerns. Narratives or storytelling is a fundamental experience formed by individuals to understand and make sense of the world around them. The creation of personal narratives has been associated with several health benefits, including an increased sense of self-efficacy, increased social support, and improved mental and physical health. Critical Narrative Intervention (CNI) is a distinct approach for marginalized communities to create a group narrative that has been found to increase empowerment and social support for participants. Recent CNI research methods have focused on sexuality and sexual health, mothering and substance use, and reproductive justice.

However, the use of CNs as an elicitation strategy has not been examined for increasing mental health treatment seeking within SGM EA of color; therefore, this pilot study will examine CNs from SGM EA of color and it's the potential to increase empowerment (including self-efficacy) and reduce mental health symptoms (depression and anxiety) as an elicitation strategy for increasing intentions to seek support (personal and professional). The proposed pilot study will also examine the feasibility, acceptability, and appropriateness of critical narratives as a strategy for SGM racial/ethnic minorities and address mental health disparities.

CHARACTERISTICS OF THE STUDY POPULATION:

1. Target Population and Accrual:

The target population for this study includes sexual and gender minority emerging adults of color who identify as living with depression in the United States. For the proposed study, we expect to screen about 200 individuals over the 6 months and consent and randomize 30 participants in a 1:1 assignment.

2. Key Inclusion Criteria:

1) identify as a sexual minority; (2) live in the United States; (3) identify as a person of color; (4) be aged 18-24 years; (5) have a smartphone and or computer access; (6) identify as living with moderate to severe depression as indicated on the PHQ-9 (score of 10 or higher); and (7) do not report suicidal ideation in the past month.

3. Key Exclusion Criteria:

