(1) Identifies as cisgender heterosexual man or woman, (2) Does not live in the United States; (3) Identifies as non-Hispanic white or Caucasian; (4) Is not between the ages of 18-24 years (inclusive) (5) Does not have access to a smartphone or computer (6) Plan to move out of the United States for the next six months (7) Does not consent to study procedures (8) Meets criteria for an unmanaged psychotic disorder (9) meets criteria for none to mild depression on the PHQ-9 (score of 9 or less), and/or (10) reports suicidal ideation in the past month.

4. Subject Recruitment and Screening:

We will leverage recruiting participants from a concurrent study testing the preliminary efficacy of a digital intervention to reduce suicidal ideation among sexual and gender minority emerging adults in the United States. The Suicide Prevention Intervention for Vulnerable Emerging Minorities (IRB Protocol: 849500) recruits and screens similar participants as the current pilot study (emerging adults ages 18-24 who identify as a sexual and gender minority). Participants who answer the Suicide Prevention Intervention eligibility screener also indicate if they may be interested in participating in other studies. Given our inclusion criteria, we hope to contact participants excluded from the Suicide Prevention Intervention and invite them to screen for this pilot study. We will contact individuals via email and ask if they would be interested in the current critical narrative pilot study. Individuals will receive a link or QR code to complete the eligibility screener.

We will also utilize social media to reach the population living within the United States on sites including Facebook, Instagram, and Dating Apps (i.e., grindr). Ads targeting within social media sites will allow us to specify the age range and other sociodemographic characteristics of individuals who will see the ads based on the information they provide in their online profiles. We will develop ads that promote our target population's interest by including diverse images of youth (i.e., images of different ages, portraying diverse race/ethnicity), as well as using ad-targeting specific to socio-demographic characteristics (e.g., delivering Facebook/Instagram ads only to youth living in our regions based on their age, race/ethnicity and sex) and interests (e.g., TV shows with LGBT themes).

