Using online recruitment methods where the intervention is not pitched by a recruiter minimizes the risk of potential coercion. Instead, SGM EA of color can choose and click on the recruitment advertisement and decide if they wish to learn more. Similarly, staff will be trained to discuss all elements of the consent process with potential participants. Consent documents will fully explain the study procedures, potential risks, and potential benefits. Participants will also be reminded that the study participation is voluntary and that refusing to participate in the study or withdrawing from the study is an option at any time.

STUDY DESIGN:

Critical narratives have not been examined for addressing psychological outcomes (e.g., depression, anxiety, self-esteem, empowerment, psychological well-being) within SGM EA of color; therefore, this pilot study will examine the use of CNIs to impact SGM of color psychological outcomes. Prior literature has shown that CNIs have the potential to increase

empowerment, self-efficacy, and social support as a prevention strategy for mental health. The study design will utilize mixed methods to address two aims:

- Aim 1) Examine the experiences of discrimination and acceptance of SGM EA of color living with depression and its impact on seeking mental health treatment,
- Aim 2) Evaluate the change in psychological and well-being outcomes (depression, anxiety, self-esteem, empowerment, and psychological well-being) of SGM individuals of color after each CNI assignment.
- Aim 3) Understand the acceptability, appropriateness, and feasibility of critical narrative development as an intervention for SGM EA of color.

Below is a timeline of the study, including study assessments and how they address one of the three aims:

Critical Narrative Intervention Timeline and Study Design			
Month(s)	Timepoint	Measure/Study Procedure	Aim(s) Addressed
1-6	Recruitment	Eligibility Screener	N/A
2-8	Baseline	Baseline Survey (n=30) Individual Interview (n=30) Randomization Photo-novella, n=15 Digital storytelling, n=15	Aim 2 Aim 1
3-10	1-month	1-Month Follow-up Survey (n=30) Individual Interview (n=30)	Aim 2 and Aim 3 Aim 3

The entire study will last about 10 months from recruitment to final collection of all critical narratives. A participant's time in the study will last about one month from enrollment during baseline to completion of the post-intervention visit and presentation of their critical narrative.

METHODS:

1. Study Instruments:

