
Potential participants interested in participating in the study will first complete an eligibility screener. Those participants that are deemed eligible based on inclusion/exclusion criteria will be contacted by a study team member to schedule a virtual baseline visit.

Participants will complete 2 online surveys during the study: at baseline and after completion of the critical narrative development (about 1 month after initial enlistment into the study). Assessments will take 20-25 minutes to complete. The primary goal of the two surveys will be to assess the preliminary effectiveness of the critical narratives at impacting depression, anxiety, self-esteem, psychological well-being, and empowerment. All surveys will be housed and implemented through REDCap. Below is a table of the measures utilized in the surveys.

Construct	Measure	Description	Citation	Time Point	
				Baseline	1-Month
Depression Symptoms	Patient Health Questionnaire (PHQ-9)	The PHQ-9 is a 9-item depression symptom checklist scored from 0 to 3 on a Likert scale of "not at all" to "nearly every day." The PHQ-9 has demonstrated high internal reliability ($\alpha = .88$) and test-retest reliability ($\alpha = .94$)	Kroenke, K., Spitzer, R.L., & Williams, J.B. (2001). The PHQ-9: Validity of a brief depression severity measure. Journal of General Internal Medicine , 16(9), 606-613.	X	X
Anxiety Symptoms	Generalized Anxiety Disorder (GAD-7)	The GAD-7 is a 7-item measure designed to assess anxiety symptoms scored from 0 to 3 on a Likert scale of "not at all" to "nearly every day," with total scores ranging from 0 to 21. The	Spitzer, R.L., Kroenke, K., Williams, J.B., & Lowe, B. (2006). A brief measure for assessing generalized anxiety disorder: the GAD-7.	X	X

		GAD-7 is valid with intercorrelations with the PHQ-2 ($r = .64$) and the Rosenberg Self-Esteem Scale ($r = .43$) and has good reliability ($\alpha = 0.89$; Lowe et al., 2008).	Archives of internal medicine, 166 (10), 1092-1097.		

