Participants provide consent for the research team to retain email addresses and phone numbers for participant follow-up. During the baseline visit, participants will be scheduled for a 1-month follow-up visit, including an interview, survey, and final submission of the critical narrative. A week before the scheduled 1-month follow-up, a research team member will reach out to the participant to confirm the 1-month study visit via phone, e-mail, or text as indicated in the participant's preferred contact method. A research team member will reach out every two days for confirmation until received from the participant. This will aid in ensuring confirmation of the scheduled follow-up and retention of participants at the follow-up time point.

STUDY PROCEDURES:

Detailed Description:

The research activities involve a two-arm pilot enrolling a sample of 30 participants who identify as SGM, POC, and living with moderate to severe depression. After consent and completion of the baseline survey (15-20 min) and interview (45-60 min), participants will be randomized into one of two critical narrative interventions: photo-novella (n=15) or digital storytelling (n=15).

All participants will be given the same two prompts for their narrative intervention asking, "Share an experience of when you have felt seen as an SGM Person of Color." AND "share an experience of when you have felt unseen as an SGM person of color."

Photo-Novella: Participants in the photo-novella intervention will be asked to tell their story through 12 photographs and a caption (6 for the first prompt and 6 for the second prompt). Participants will be instructed to take a photograph answering the two prompts. Participants may use their smartphones or digital camera to capture their photographs. Participants may also edit their photographs using photo-editing software for aesthetics. Participants will also be asked to provide a short caption (no more than two sentences) explaining their photograph and provide a title for their work. Participants will be provided with a basic guide on photography and how to "snap a picture."

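### Inclusion criterion 1 requires a sexual-minority identity, which shuts out heterosexual gender-minority adults of color who belong to the stated study population

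*Combined protocol and SAP*

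**What the plan says.** The Introduction and Purpose introduces the abbreviation with "Youth who identify as sexual and/or gender minorities (SGM", and its next mention of stigma again treats sexual minority and gender minority as two categories joined by and/or. Later in the same section the participants are described: "Participants for this pilot are emerging adults living with depression who self-identify as both an SGM and a racial/ethnic minority". Section 1, Target Population and Accrual, says "The target population for this study includes sexual and gender minority emerging adults of color". The Detailed Description under Study Procedures speaks of "enrolling a sample of 30 participants who identify as SGM, POC, and living with moderate to severe depression". The study title, the aims and both narrative prompts use the same term.

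Section 2, Key Inclusion Criteria, begins: "1) identify as a sexual minority; (2) live in the United States; (3) identify as a person of color". The four remaining items cover age, device access, PHQ-9 score and absence of recent suicidal ideation. None mentions gender identity.

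Section 3, Key Exclusion Criteria, begins: "1) Identifies as cisgender heterosexual man or woman".

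On how the lists are used, Methods section 1 (Study Instruments) says: "Those participants that are deemed eligible based on inclusion/exclusion criteria will be contacted by a study team member". The Consent Process section likewise has people contacted once they meet the inclusion criteria.

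One place uses narrower wording. Section 8, Investigator's Risk/Benefit Assessment, refers to the study population as sexual minorities only.

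**The concern.** The eligibility rule and the population statement do not describe the same people. The rule tests sexual orientation alone, while the stated population can be entered through orientation, gender identity or both. The group in the gap is gender-minority adults of color who identify as heterosexual.

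This matters most for Aim 1, which is to "Examine the experiences of discrimination and acceptance of SGM EA of color living with depression and its impact on seeking mental health treatment". That aim rests on baseline interviews that ask about sexual identity and gender identity alike. If one part of the SGM population cannot enter, the interviews carry nothing from it, and conclusions worded for SGM emerging adults of color reach further than the sample. Gender-minority experience would be narrowed rather than absent, because gender-minority people who are also sexual minorities remain eligible. The same limit applies to the Aim 2 and Aim 3 findings.

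**Working it through.** The plan has no figure to reproduce here, and no sample-size or error-rate calculation is involved. The check is logical. A person is eligible only if inclusion 1 is met and exclusion 1 is not, since the protocol applies both lists. The stated population is taken from the Introduction's and/or definition.

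| Gender identity and orientation | In stated SGM population | Meets inclusion 1 | Hit by exclusion 1 | Eligible on these items |
|---|---|---|---|---|
| Cisgender, heterosexual | No | No | Yes | No |
| Cisgender, sexual minority | Yes | Yes | No | Yes |
| Gender minority, sexual minority | Yes | Yes | No | Yes |
| Gender minority, heterosexual | Yes | No | No | **No** |

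Three rows are in the stated population, two of them are eligible, and 3 − 2 = 1 is omitted. Only the last row is a mismatch.

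Does another reading of the population remove the mismatch?

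- *And/or (Introduction):* the population is rows 2 to 4. Inclusion 1 omits row 4.
- *And, read as requiring both identities (a strict reading of the target statement):* the population is row 3 alone. Inclusion 1 then admits row 2, which would be outside it.
- *Sexual minorities only (Risk/Benefit wording):* the population is rows 2 and 3, which matches inclusion 1. It then contradicts the definition, the participant descriptions and the title.

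No reading of the term SGM agrees with inclusion 1.

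The two lists can also be compared with each other. Each of the seven inclusion items has a counterpart among the exclusions:

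- Exact complements: 2/2 (US residence), 4/4 (age 18-24), 5/5 (device), 6/9 (PHQ-9 of 10 or more against 9 or less) and 7/10 (suicidal ideation in the past month). That is 5 of 7.
- Near complement: 3/3 (person of color against non-Hispanic white or Caucasian).
- Not a complement: 1/1. Row 4 fails the inclusion item and is not named in the exclusion item.

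In exclusion 1 the word cisgender has a purpose only if heterosexual gender-minority people could otherwise be eligible. Inclusion 1 already bars every heterosexual person, so the word has no effect.

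**The case against.** The strongest reply is that inclusion 1 is shorthand. Sexual minority is never defined. The Risk/Benefit section uses the term for the whole population, and the very sentence that introduces SGM compares SGM youth with heterosexual peers, so the authors' labels are loose. Exclusion 1 and the recruitment text suggest that gender minorities of any orientation were meant to be eligible. The lists are headed as key criteria, and the REDCap screener that applies them is not in the documents, so nobody may in fact be turned away.

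This is plausible, and it limits what can be said about practice. It does not repair the text. The Introduction separates the two terms, and an eligibility criterion is not the place for shorthand. If staff did enroll a heterosexual gender-minority person, they would depart from the written criterion. If the wording is a slip, the correction is one line.

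A second reply is that the consequence is modest: this is an exploratory pilot with 15 per arm, no power analysis and no stated analysis by gender identity or orientation. That is fair and it bounds the severity. The count of three, two and one must not be read as a third of the target being lost, because the cells are not equally common and their sizes are not given. Nor is it an error in itself that two eligibility lists fail to mirror each other; the error is that they disagree about this group.

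**Conclusion.** The concern holds. As written, inclusion 1 conflicts with the SGM population stated in the Introduction, the target statement and the Study Procedures, and with exclusion 1. One of three identity categories in the stated population cannot enroll.

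The number of people affected is unknown. The 30 places could still be filled, so the effect is on the composition of the sample and the reach of the conclusions, not on sample size, randomization or outcome measurement. The verdict assumes that the screener follows inclusion 1 literally and that SGM carries its and/or meaning. The wording conflict is certain; whether anyone is excluded in practice, and which population the sponsor intends, cannot be settled from the documents.

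**What to change.** State which population is meant and bring the passages into line.

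- **If SGM is meant:** change inclusion 1 to *identify as a sexual and/or gender minority*, which is the complement of exclusion 1. Make the REDCap screener logic match and align the Risk/Benefit wording. The cost is a minor amendment, and the eligible pool widens. As an optional further step, check how orientation-framed material suits heterosexual gender-minority participants: the QPIAS introduction refers to LGBQA+ identity, and the LGBTQ+ PCMS-B has a heterosexism subscale. The protocol says the instruments will not be changed, so any poor fit would be handled by a note on interpretation. The item wording is not in the documents, so poor fit is only a possibility.
- **If only sexual minorities are meant:** keep inclusion 1 and narrow the title, target statement, participant descriptions, aims, exclusion 1 and the wording of the conclusions. This means more edits, and the results would then be claimed for a smaller population.

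If screening has already begun, confirm how the screener treated this group and report it with the results.
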